8.6. Pharmacokinetic Analysis

Plasma concentrations of ENTO and/or its metabolites (if applicable) over sampling time will be listed and summarized by hepatic function group and smoking status (Cohort 1 only).

Plasma concentrations of ENTO and/or its metabolites (if applicable) over time will be plotted in semi-logarithmic and linear formats as mean \pm SD and as median (Q1, Q3).

The PK parameters will be listed and summarized for ENTO and/or its metabolites (if applicable) using descriptive statistics (e.g., sample size, arithmetic mean, geometric mean, % CV, SD, median, minimum, and maximum) by hepatic function group (normal or CPT Class A, B, or C) and smoking status (Cohort 1 only).

A parametric (normal theory) ANOVA model appropriate for a parallel design will be fitted to the natural logarithmic transformation of PK parameters (AUC_{τ} and C_{\max}) for ENTO and/or its metabolites (if applicable). The 90% CIs will be constructed for the GLSM ratios of PK parameters for ENTO and/or its metabolites (if applicable) in each hepatic impairment group versus the matched control (normal hepatic function) group (and for Cohort 1, stratified by smoking status). The 90% CIs will be examined to determine if the GLSM ratio is within limits of 50% to 200%.

ENTO percent protein binding will be summarized by hepatic function group and smoking status (Cohort 1 only), and data for individual subjects will be presented in a listing (if applicable).

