8.7. Sample Size

A sample size of 8 evaluable subjects per hepatic function group (for Cohort 1, it is 8 evaluable subjects per hepatic function group within each smoking status group) will provide

a \geq 89% probability for the 90% CI for the GLSM ratio of pharmacokinetic parameters (AUC or C_{\max}) for ENTO in the hepatic impairment/dysfunction group(s) versus the appropriate group of matched controls, to be within limits of 50% to 200%. The calculation assumes an expected ratio of geometric means of 1.0 in pharmacokinetic parameters and inter-subject standard deviation of 0.455 for the natural logarithm-transformed pharmacokinetic parameters for ENTO. The assumption is based on the data obtained from a prior clinical study of ENTO (Study GS-US-339-0111).

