**Figure 1-2. Study Schema – All Cohorts**

#### **1.4. Sample Size and Power**

Eight evaluable subjects per hepatic function group (for Cohort 1, it is 8 evaluable subjects per hepatic function group within each smoking status group) will provide  $\geq 89\%$  probability for the 90% confidence interval (CI) for the geometric least-squares mean (GLSM) ratio of PK parameters (AUC or  $C_{\max}$ ) for ENTO in the hepatic impairment/dysfunction group(s) versus the appropriate group of matched, healthy controls, to be within limits of 50% to 200%. The calculation assumes an expected ratio of geometric least-squares means of 1.0 in PK parameters and inter-subject standard deviation of 0.455 for the natural logarithm-transformed pharmacokinetic parameters for ENTO. The assumption is based on the data obtained from a prior clinical study of ENTO (Study GS-US-339-0111).

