### **2.3. Changes from Protocol-Specified Analysis**

No changes from protocol-specified analyses are planned.

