The ESTIMATE statement will be used to produce the point estimate and 90% CI on natural-log scale for the differences between hepatic function groups/smoking groups. The test/reference comparison ratio and associated 90% CI will be calculated by exponentiation of the natural-log scale point estimate and the corresponding lower and upper limits.

Ninety percent CIs for the GLSM ratio of the test and reference groups will be calculated for each ENTO and/or its metabolites (if applicable) PK parameter in each cohort, consistent with the 2 one-sided t-tests approach {[U.S. Department of Health and Human Services Food and Drug Administration Center for Drug Evaluation and Research \(CDER\) 2001](#), U.S. Department of

Health and Human Services Food and Drug Administration Center for Drug Evaluation and Research (CDER) 2003}. For the comparison between hepatic function groups: if the upper bound of the 2-sided 90% CI of the GLSM ratio for  $AUC_{\tau}$  and  $C_{\max}$  (Day 5) is smaller than 2.0, we will reject the hypothesis that subjects with moderate (or mild or severe as applicable) hepatic impairment exhibit average PK parameter (ie,  $AUC_{\tau}$  and  $C_{\max}$  [Day 5]) increases of at least 100% for analyte ENTO and/or its metabolites (if applicable) compared with subjects with normal liver function.

The PK parameters  $T_{1/2}$ ,  $CL/F$  and  $V_z/F$  will be compared between hepatic function groups (for Cohort 1: the comparison between hepatic function groups will be by smoking status groups) using a nonparametric method of Wilcoxon rank sum test. The following SAS® PROC NPAR1WAY code will be used for such nonparametric comparison.

```
proc npar1way wilcoxon;  
  class hepgrp;  
  var aval;  
run;
```

To evaluate the protein binding of ENTO and/or its metabolites, the percent of unbound ENTO and/or its metabolites at  $T_{\max}$  and another later time point will be summarized by hepatic function group and smoking status group (Cohort 1 only). Protein binding data for individual subject will be presented in a listing.

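### The stated probability of at least 89% fits an upper-limit-only criterion; for the 50%–200% criterion it describes, the figure is about 79%, and the protocol and SAP apply different rules

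*Protocol*

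**What the plan says.** Protocol 8.7 opens with "A sample size of 8 evaluable subjects per hepatic function group" (in Cohort 1, per hepatic function group within each smoking stratum). It claims at least "89% probability for the 90% CI for the GLSM ratio of pharmacokinetic parameters" (AUC or Cmax), impaired versus matched controls, "to be within limits of 50% to 200"%. It adds: "The calculation assumes an expected ratio of geometric means of 1.0 in pharmacokinetic parameters", with an inter-subject SD of 0.455 on the log scale taken from a prior study. The Synopsis repeats the statement, and SAP 1.4 does too: "matched, healthy controls, to be within limits of 50% to 200"%.

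On the analysis, Protocol 8.6 says: "The 90% CIs will be examined to determine if the GLSM ratio is within limits of 50% to 200"%. SAP 5.2.2 builds a two-sided 90% CI and refers to the two one-sided t-tests approach. The one decision rule it then states depends on the upper bound being below 2.0, in which case "we will reject the hypothesis that subjects with moderate (or mild or severe as applicable) hepatic impairment exhibit average PK parameter" increases of 100% or more. It states no rule for the lower bound. SAP 2.3 reads: "No changes from protocol-specified analyses are planned".

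**The concern.** A CI lying within 50%–200% is a two-sided event: the lower limit must exceed 50% and the upper limit must be below 200%. When the true ratio is 1.0, each side is equally likely to fail, so the two-sided probability must be clearly lower than the one-sided one. The stated 89% looked too high for 8 per group with an SD of 0.455, and the upper-limit rule in SAP 5.2.2 suggested where it came from.

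Two things are at stake. First, this is the only quantitative justification for the size of any cohort. Second, the two rules can give opposite conclusions from the same data. Protocol 1.3 reports lower exposure in Cohort 1 smokers, and Protocol 4.3.3 requires all healthy controls to abstain from nicotine. The smoker stratum therefore compares impaired smokers with non-smoking controls, and a ratio below 1 is plausible there. A CI lying wholly below 50% fails Protocol 8.6 but satisfies SAP 5.2.2. The meaningful change in Protocol 3.1 is a difference of at least 2-fold, with no direction specified.

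**Working it through.** **Inputs**
- n = 8 evaluable per group, true ratio 1.0, SD 0.455 on the log scale, 90% CI, limits 50%–200% (Protocol 8.7, SAP 1.4).
- Parallel-group ANOVA on log-transformed parameters (Protocol 8.6), so df = 8 + 8 − 2 = 14.

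**Common quantities**
- SE = 0.455 × √(2/8) = 0.2275.
- Margin = ln 2 = 0.693; margin/SE = 0.693/0.2275 = 3.047.
- t(0.95, 14) = 1.761.

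**Reproducing the plan's figure: upper limit only.** The probability that the upper 90% limit is below 200% is the probability that a noncentral t variable with 14 df and noncentrality 3.047 exceeds 1.761. This is **89.4%**, which agrees with the stated figure.

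**The criterion as written: both limits.** With a true ratio of 1.0, each side fails with probability 1 − 0.8943 = 0.1057, and both failing together is negligible. Hence P ≈ 1 − 2 × 0.1057 = 0.789. Exact integration over the distribution of the sample variance also gives **78.9%**. A simulation of 400,000 trials gave 78.9% for both limits and 89.4% for the upper limit.

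**Could another reading give 89% for both limits at 8 per group?**

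| Reading | Both limits inside 50%–200% |
|---|---|
| Normal approximation | 83.9% |
| t critical value with normal distribution | 80.1% |
| Separate group variances (Welch simulation, approximating the SAP 5.2.2 model) | 78.3% |
| Variance pooled over more groups (28–60 df) | 81.6%–82.9% |
| 0.455 read as a CV (SD 0.434) | 83.6% |
| Paired, SD of difference 0.455 × √2 | 72.6% |

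None comes within 2 points of 89%. The readings that do reach it contradict the stated inputs: an 80% CI (90.6%), 8 versus 16 subjects (92.2%), 0.455 as the SD of a paired difference (97.3%), or 10 per group (89.7%).

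**What the two-sided criterion would need.** At SD 0.455, 9 per group gives 85.2% and 10 per group gives 89.7%. With 8 per group, the SD would have to be about 0.406 or less.

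**Joint success.** The plan's statement is per parameter. If AUCtau and Cmax both had to meet the two-sided criterion, the probability would be about 65%–72% for correlations of 0.5–0.9. Those correlations are assumed; neither document gives one.

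**The case against.** The documents give no formula, so the one-sided origin of 89% is an inference. A two-sided calculation with the 10 enrolled per group gives 89.7%, which would also satisfy the stated bound. That is fair: the one-sided figure matches but is not proven to be the source. It does not rescue the sentence, which ties the figure to 8 evaluable subjects. It does mean that 79% is the value at the planned minimum, rising to about 90% if all 10 per group are evaluable.

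A second objection is that little depends on the percentage. This is a non-randomized Phase 1 study reporting ratios with 90% CIs, and those estimates are the same whatever probability is printed. Cohort 3 opens on a mean difference of at least 2-fold and Cohort 2 on safety and PK findings, so neither gate uses this probability. This stands as a limit on the consequences. It does not make the figure right.

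A third is that SAP 5.2.2 does not expressly drop the 50% limit. It formalises one side, still reports the lower limit, and SAP 1.4 keeps the 50%–200% wording. The smoking effect also has its own comparison in SAP 5.2.2, and lower exposure in smokers is not evidence that hepatic impairment lowers exposure. All of that is correct. Even so, the SAP's only decision rule ignores the lower limit, Protocol 8.6 does not, and SAP 2.3 denies any difference.

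**Conclusion.** The concern holds. For the criterion stated, the probability is 78.9% rather than at least 89%, an overstatement of about 10 points. The chance of missing the criterion when there is no true effect is about 21%, roughly double the implied 11%. This rests on the plan's own inputs (8 per group, log SD 0.455, ratio 1.0, 90% CI) and a pooled-variance parallel-group analysis; the SAP's separate-variance model changes it only to about 78.3%. That the figure came from the upper-limit calculation is the likely explanation, supported by the match at 89.4% and by the SAP's rule. Independently of how 89% was obtained, the protocol and SAP state different decision rules, and the SAP's own sample-size section does not match its analysis section.

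**What to change.** Choose one rule and make the probability fit it, in one of two ways:

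- **Keep the two-sided criterion.** Restate the probability in the Synopsis, Protocol 8.7 and SAP 1.4 as about 79% for 8 evaluable per group, and add the lower-limit condition (above 50%) to SAP 5.2.2.
- **Adopt the upper-limit rule.** State in the same three places that at least 89% is the probability that the upper 90% limit is below 200%. Change Protocol 8.6 to match, and say how a fall in exposure below 50% will be interpreted.

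In either case use the same rule in Protocol 8.6 and SAP 5.2.2, and list in SAP 2.3 any departure from the protocol that remains. The cost is wording in the two documents. No subjects need be added; the only loss is a less favourable stated figure if the two-sided criterion is kept.

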9. RESPONSIBILITIES

9.1. Investigator Responsibilities

9.1.1. Good Clinical Practice

The investigator will ensure that this study is conducted in accordance with the principles of the Declaration of Helsinki (as amended in Edinburgh, Tokyo, Venice, Hong Kong, and South Africa), International Conference on Harmonisation (ICH) guidelines, or with the laws and regulations of the country in which the research is conducted, whichever affords the greater protection to the study subject. These standards are consistent with the European Union Clinical Trials Directive 2001/20/EC and Good Clinical Practice Directive 2005/28/EC.

The investigator will ensure adherence to the basic principles of Good Clinical Practice, as outlined in 21 CFR 312, subpart D, "Responsibilities of Sponsors and Investigators," 21 CFR, part 50, "Protection of Human Subjects", and 21 CFR, part 56, "Institutional Review Boards".

The investigator and all applicable subinvestigators will comply with 21 CFR, Part 54, "Financial Disclosure by Clinical Investigators", providing documentation of their financial interest or arrangements with Gilead, or proprietary interests in the study drug under study. This documentation must be provided prior to the investigator's (and any subinvestigator's) participation in the study. The investigator and subinvestigator agree to notify Gilead of any change in reportable interests during the study and for 1 year following completion of the study. Study completion is defined as the date when the last subject completes the protocol-defined activities.

9.1.2. Institutional Review Board (IRB)/Independent Ethics Committee (EC) Review and Approval

The investigator (or Sponsor as appropriate according to local regulations) will submit this protocol, informed consent form, and any accompanying material to be provided to the subject (such as advertisements, subject information sheets, or descriptions of the study used to obtain informed consent) to an IRB/EC. The investigator will not begin any study subject activities until approval from the IRB/IEC has been documented and provided as a letter to the investigator.

Before implementation, the investigator will submit to and receive documented approval from the IRB/EC any modifications made to the protocol or any accompanying material to be provided to the subject after initial IRB/EC approval, with the exception of those necessary to reduce immediate risk to study subjects.

9.1.3. Informed Consent

The investigator is responsible for obtaining written informed consent from each individual participating in this study after adequate explanation of the aims, methods, objectives, and potential hazards of the study and before undertaking any study-related procedures. The

investigator must use the most current IRB- or EC-approved consent form for documenting written informed consent. Each informed consent (or assent as applicable) will be appropriately signed and dated by the subject or the subject's legally authorized representative and the person conducting the consent discussion, and also by an impartial witness if required by IRB or EC or local requirements.

9.1.4. Confidentiality

The investigator must assure that subjects' anonymity will be strictly maintained and that their identities are protected from unauthorized parties. Only subject initials, date of birth, another unique identifier (as allowed by local law) and an identification code will be recorded on any form or biological sample submitted to the Sponsor, IRB/EC, or laboratory. Laboratory specimens must be labeled in such a way as to protect subject identity while allowing the results to be recorded to the proper subject. Refer to specific laboratory instructions or in accordance with local regulations. NOTE: The investigator must keep a screening log showing codes, names, and addresses for all subjects screened and for all subjects enrolled in the trial. Subject data will be processed in accordance with all applicable regulations. Only subject initials or dummy initials (in required regions), date of birth, another unique identifier (as allowed by local law), and an identification code will be included for applicable regions.

The investigator agrees that all information received from Gilead, including but not limited to the investigator brochure, this protocol, CRF/eCRF, the study drug, and any other study information, remain the sole and exclusive property of Gilead during the conduct of the study and thereafter. This information is not to be disclosed to any third party (except employees or agents directly involved in the conduct of the study or as required by law) without prior written consent from Gilead. The investigator further agrees to take all reasonable precautions to prevent the disclosure by any employee or agent of the study site to any third party or otherwise into the public domain.

9.1.5. Study Files and Retention of Records

The investigator must maintain adequate and accurate records to enable the conduct of the study to be fully documented and the study data to be subsequently verified. These documents should be classified into at least the following two categories: (1) investigator's study file, and (2) subject clinical source documents.

The investigator's study file will contain the protocol/amendments, CRF and query forms, IRB/EC and governmental approval with correspondence, informed consent, drug records, staff curriculum vitae and authorization forms, and other appropriate documents and correspondence.

The required source data should include sequential notes containing at least the following information for each subject:

- Subject identification (name, date of birth, gender). Only subject initials or dummy initials (in required regions), another unique identifier (as allowed by local law), and an identification code will be included for applicable regions

- Documentation that subject meets eligibility criteria, ie, history, physical examination, and confirmation of diagnosis (to support inclusion and exclusion criteria);
- Documentation of the reason(s) a consented subject is not enrolled
- Participation in study (including study number);
- Study discussed and date of informed consent;
- Dates of all visits;
- Documentation that protocol specific procedures were performed;
- Results of efficacy parameters, as required by the protocol;
- Start and end date (including dose regimen) of study drug, including dates of dispensing and return;
- Record of all AEs and other safety parameters (start and end date, and including causality and severity);
- Concomitant medication (including start and end date, dose if relevant; dose changes);
- Date of study completion and reason for early discontinuation, if it occurs.

All clinical study documents must be retained by the investigator until at least 2 years or according to local laws, whichever is longer, after the last approval of a marketing application in an ICH region (ie, United States, Europe, or Japan) and until there are no pending or planned marketing applications in an ICH region; or, if no application is filed or if the application is not approved for such indication, until 2 years after the investigation is discontinued and regulatory authorities have been notified. Investigators may be required to retain documents longer if specified by regulatory requirements, by local regulations, or by an agreement with Gilead. The investigator must notify Gilead before destroying any clinical study records.

Should the investigator wish to assign the study records to another party or move them to another location, Gilead must be notified in advance.

If the investigator cannot provide for this archiving requirement at the study site for any or all of the documents, special arrangements must be made between the investigator and Gilead to store these records securely away from the site so that they can be returned sealed to the investigator in case of an inspection. When source documents are required for the continued care of the subject, appropriate copies should be made for storage away from the site.

9.1.6. Case Report Forms

For each subject consented, an eCRF will be completed by an authorized study staff member whose training for this function is documented according to study procedures. eCRF should be completed on the day of the subject visit to enable the sponsor to perform central monitoring of

safety data. The Eligibility Criteria eCRF should be completed only after all data related to eligibility have been received. Subsequent to data entry, a study monitor will perform source data verification within the EDC system. Original entries as well as any changes to data fields will be stored in the audit trail of the system. Prior to database lock (or any interim time points as described in the clinical data management plan), the investigator will use his/her log in credentials to confirm that the forms have been reviewed, and that the entries accurately reflect the information in the source documents. The eCRF capture the data required per the protocol schedule of events and procedures. System-generated or manual queries will be issued to the investigative site staff as data discrepancies are identified by the monitor or internal Gilead staff, who routinely review the data for completeness, correctness, and consistency. The site coordinator is responsible for responding to the queries in a timely manner, within the system, either by confirming the data as correct or updating the original entry, and providing the reason for the update (e.g. data entry error). At the conclusion of the trial, Gilead will provide the site with a read-only archive copy of the data entered by that site. This archive must be stored in accordance with the records retention requirements outlined in Section 9.1.5.

9.1.7. Study Drug Accountability and Return

Gilead recommends that used and unused study drug supplies be returned to the shipping facility from which it came for eventual destruction. The study monitor will provide instructions for return. If return is not possible, the study monitor will evaluate each study center's study drug disposal procedures and provide appropriate instruction for destruction of unused study drug supplies. If the site has an appropriate standard operating procedure (SOP) for drug destruction as determined by Gilead QA, the site may destroy used (empty or partially empty) and unused study drug supplies in accordance with that site's approved SOP. A copy of the site's approved SOP will be obtained for central files.

If study drug is destroyed on site, the investigator must maintain accurate records for all study drug destroyed. Records must show the identification and quantity of each unit destroyed, the method of destruction, and the person who disposed of the study drug. Upon study completion, copies of the study drug accountability records must be filed at the site. Another copy will be returned to Gilead.

The study monitor will review study drug supplies and associated records at periodic intervals.

